6.2 Analyses of Key Secondary Efficacy Endpoints

Similarly to the primary endpoint, each secondary endpoint will be summarized by treatment group. Subjects with the intercurrent events defined in Section 2.2 and/or missing key secondary endpoint data at the Week 52 visit are considered failures. Each of the key secondary endpoints will be analyzed using the same approach as described for the primary efficacy endpoint using the following hypothesis:

$$H_0: \delta = 0$$

$$H_1: \delta \neq 0$$

Where δ is the common treatment difference across strata, $j=1$ to m . The common treatment difference is a weighted average of the stratum-specific treatment differences.

The estimate of the common treatment difference along with the corresponding stratified Newcombe 95% CI using the method of Yan and Su (2010) and CMH p-value will be presented for each active treatment group to corresponding placebo group (25 mg in induction placebo group or 75 mg in induction placebo group; placebo groups are not pooled) comparison.

The key secondary efficacy endpoints are:

- Endoscopic remission, as defined by centrally read endoscopic subscore 0 or 1 (modified, excludes friability), at the Week 52 visit.
- Clinical remission as defined by stool frequency subscore of 0 or 1 with at least a 1-point change from induction study (SHP647-301 or SHP647-302) baseline in SF subscore, and RB subscore of 0, at the Week 52 visit. Subjects with missing induction baseline value in SF subscore will be counted as clinical remission if both SF and RB subscores are 0 at Week 52.
- Sustained remission, ie, in remission at the SHP647-303 Week 52 visit, among subjects who were in remission at the time of MNT baseline (the observed value for the efficacy assessment at Week 12 in induction study). Remission is defined in Section 6.1.
- Clinical response based on composite score at the Week 52 visit. Clinical response (composite) is defined as a decrease from induction study (SHP647-301 or SHP647-302) baseline in the composite score of subject-reported symptoms using daily e-diary and centrally read endoscopy of at least 2 points and at least 30%, with an accompanying decrease in the subscore for rectal bleeding ≥ 1 point or a subscore for rectal bleeding ≤ 1 . Subjects with missing induction baseline value in the composite score but in remission by composite score will be counted as clinical response.

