- Mucosal healing based on endoscopic and histologic assessment, at the Week 52 visit. Mucosal healing is defined by centrally read endoscopic subscore 0 or 1 (modified, excludes friability) and centrally read Geboes score of ≤ 2 .
- Glucocorticoid-free clinical remission at Week 52, among subjects using glucocorticoids at the MNT baseline. Glucocorticoid-free clinical remission is defined as clinical remission in addition to not requiring any treatment with glucocorticoids for at least 4 weeks prior to the Week 52 visit. Clinical remission is defined in second bullet above.
- Glucocorticoid-free remission at Week 52, among subjects using

glucocorticoids at the MNT baseline. Glucocorticoid-free remission is defined as remission in addition to not requiring any treatment with glucocorticoids for at least 4 weeks prior to the Week 52 visit. Remission is defined in Section 6.1.

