12.3 Definition of Visit Windows

Assessments will be assigned to visits based upon the date the assessment took place regardless of the completed CRF page. Assessments will be mapped to visits as outlined in [Table 6](#) to Table 9.

Should there be more than 1 assessment mapped into a given study visit with nonmissing results, the assessment closest to the planned visit will be used for analysis (referred to as analysis visit); in case of ties between observations, the later assessment will be used.

Study day will be calculated as follows:

- If the assessment date is on or after the date of first dose of IP:

$$\text{Study day} = \text{assessment date} - \text{first dosing date} + 1$$

- If the assessment date is before the date of first dose of IP:

$$\text{Study day} = \text{assessment date} - \text{first dosing date}$$

Table 6: Visit Windows (Study Day Based) – PRO, Partial Mayo, Vital Sign, Weight, and Endoscopy Assessments

Visit	Planned Study Day	Start Day of Window	End Day of Window
Week 4	28	2	42
Week 8	56	43	70

Week 12	84	71	98
Week 16	112	99	126
Week 20	140	127	154
Week 24	168	155	182
Week 28	196	183	210
Week 32	224	211	238
Week 36	252	239	266
Week 40	280	267	294
Week 44	308	295	322
Week 48	336	323	350
Week 52	364	351	EOT Date
Follow-up	EOT Date + 84	EOT Date +1	EOF Date

EOT=end of treatment; PRO=patient-reported outcomes; RB=rectal bleeding; SF=stool frequency
 *Endoscopy is performed only as part of the Week 52 assessments. To accommodate the scheduling of the endoscopy prior to the Week 52 visit, the start day of the analysis window will be extended to >342 for this parameter only if there is a valid assessment of SF and RB mapped to Week 52.
 *Follow-up visit applies to vital sign and weight assessments only.

Table 7: Visit Windows (Study Day Based) – ADA Assessments

Visit	Planned Study Day	Start Day of Window	End Day of Window
Week 12	84	2	126
Week 24	168	127	210
Week 36	252	211	EOT Date

ADA=anti-drug antibody; EOT=end of treatment
 *Following the implementation of Protocol Amendment 3, ADA assessments are not performed at Week 52.

Table 8: Visit Windows (Study Day Based) – [REDACTED] and ECG Assessments

Visit	Planned Study Day	Start Day of Window	End Day of Window
Week 12	84	2	126
Week 24	168	127	266
Week 52	364	267	EOT Date

ECG=electrocardiogram; EOT=end of treatment; [REDACTED]

Table 9: Visit Windows (Study Day Based) – Safety Lab, Physical Examination, and Neurological Testing Assessments

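### Endoscopies on Days 343–350 count as Week 52 only with valid diary scores, so endpoints that use no diary data at Week 52 can be scored failure for a diary gap

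*SAP*

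**What the plan says.** **Mapping.** SAP 12.3 states: "Assessments will be assigned to visits based upon the date the assessment took place regardless of the completed CRF page". Table 6 gives the windows "Week 48 336 323 350" and "Week 52 364 351 EOT Date" (visit, planned day, first day, last day).

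**Exception.** The Table 6 footnote explains that "Endoscopy is performed only as part of the Week 52 assessments". To allow for scheduling the endoscopy ahead of the visit, its window start is "extended to >342 for this parameter only if there is a valid assessment of SF and RB mapped to Week 52".

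**Schedule.** Protocol 7.2.2.2 puts Visit 14 Part 2 on Day 364 ±10 days and Part 1, which includes the endoscopy, up to 10 days before that, preferably 5 to 7.

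**Endpoints.** The first key secondary endpoint in SAP 6.2 is "Endoscopic remission, as defined by centrally read endoscopic subscore 0 or 1 (modified, excludes friability), at the Week 52 visit". The fifth is mucosal healing: "Mucosal healing is defined by centrally read endoscopic subscore 0 or 1 (modified, excludes friability) and centrally read Geboes score" of at most 2. The Week 52 component of sustained endoscopic remission (SAP 6.3) is the endoscopic subscore alone.

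**Missing data.** For key secondary endpoints, "Subjects with the intercurrent events defined in Section 2.2 and/or missing key secondary endpoint data at the Week 52 visit are considered failures". SAP 6.3 applies the same rule to missing Week 52 data for other secondary endpoints.

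**The concern.** The footnote makes the use of an endoscopy depend on a different measurement. For the primary endpoint, clinical response and Mayo remission this changes nothing, because they need SF and RB and fail without them. For the three endpoints above, a centrally read endoscopy taken on schedule is set aside and the subject becomes a nonresponder for a reason unrelated to the endpoint. A diary gap is not among the intercurrent events in SAP Table 1, which are treatment failure, rescue therapy and discontinuation.

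The rule is also uneven. If the plan meant endoscopic endpoints to require a diary, it would require one on every day, but it does so only for endoscopies before Day 351.

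Protocol 3.1.2 presents the first two key secondary endpoints as a separate look at endoscopy and at symptoms, in support of the composite primary. Letting missing symptom data decide the endoscopic half works against that separation.

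**Working it through.** **1. The affected band.** The midpoint of planned Days 336 and 364 is (336 + 364)/2 = 350. Week 48 therefore ends on Day 350 and Week 52 starts on Day 351, as Table 6 shows. A start of >342 means Day 343, so the conditional band is Days 343–350.

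**2. Can a compliant endoscopy fall there?** Part 2 may be on Days 354–374. The earliest Part 1 is 354 − 10 = Day 344, so Days 344–350 are reachable. With Part 2 on the planned Day 364, Part 1 is on Day 354 or later and the condition never applies.

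**3. How often?** The documents give no distribution of visit dates. Assume Part 2 is uniform over its window and count (Part 2 day, gap) pairs that put Part 1 on or before Day 350:

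| Part 2 window | Gap | Pairs | Share |
|---|---|---|---|
| ±7 days (357–371) | 5–7 days | 1/45 | 2.2% |
| ±7 days | 1–10 days | 10/150 | 6.7% |
| ±10 days (354–374) | 1–10 days | 28/210 | 13.3% |
| ±10 days | 5–7 days | 9/63 | 14.3% |

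The ±7-day rows come from SAP Appendix 16.1, the schedule before Amendment 3. They should describe most completers. Once Amendment 3 is in force, the next visit is the Week 52/ET visit, within about 4 weeks of the last one (Protocol 7.2.2.1), so only subjects already near Week 52 could complete under ±10 days.

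**4. How many outcomes change?** Further assumptions are:
- 5–10% of these subjects lack valid SF/RB at Week 52;
- enrolment kept the planned mix, giving 366 × 592/696 ÷ 4 ≈ 78 per arm;
- everyone completes;
- the SAP Table 2 rates for endoscopic remission hold (42.5% and 15%).

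Only would-be remitters change status. At the upper inputs, 0.143 × 0.10 = 0.0143 of subjects are affected:
- active: 78 × 0.0143 × 0.425 ≈ 0.47 subjects;
- placebo: 78 × 0.0143 × 0.15 ≈ 0.17 subjects;
- loss in the difference: 0.0143 × 27.5 ≈ 0.4 points.

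With 2.2% early endoscopies and 10% missing, the loss is 0.0022 × 27.5 ≈ 0.06 points. At 5% missing, both figures halve.

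**5. Power.** Power = Φ{[|p₁ − p₂| − z√(2p̄(1 − p̄)/n)] / √[(p₁(1 − p₁) + p₂(1 − p₂))/n]}, with two-sided alpha 0.025 (z = 2.241).

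Reproducing SAP Table 2 at n = 148 per arm gives 0.999 for endoscopic remission (stated 0.99) and 0.911 for mucosal healing (stated 0.91). The latter matches at alpha 0.025; at the column label of .05 it would be 0.949.

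At 78 per arm, with the same share of responders lost in both arms:

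| Endpoint | No loss | 1% lost | 2% lost |
|---|---|---|---|
| Endoscopic remission | 0.949 | 0.945 | 0.942 |
| Mucosal healing | 0.637 | 0.631 | 0.624 |

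The upper-input loss of 1.43% lies between the last two columns.

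**The case against.** The best defence is that valid Week 52 diary scores act as a date-based check that the subject reached Week 52, which keeps early-termination endoscopies out of the extended window. The need for such a check stands. But the SAP does not give this reason, and discontinuation already counts as failure in the composite definitions of SAP Table 1. The diary is also a poor proxy, since a completer can lack valid scores.

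A second defence is that scoring missing data as failure is the plan's general convention and applies equally to both arms. That is true, and it limits any bias. Here, however, the endoscopy is not missing; the mapping rule makes it so.

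A third is that the diary condition will seldom fail. Entries are daily, compliance is checked at each visit (Protocol 7.3.2.3), and the scores use only 3 of the last 10 days (SAP 12.4.1). This also stands, and it is why the effect is small.

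A reader might infer that one affected subject costs 1/78 = 1.3 points in endoscopic remission. That treats the subject as a certain remitter in one arm with no offset in the other. A non-remitter fails either way, and both arms lose a few.

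**Conclusion.** The rule is wrong as written for endoscopic remission, mucosal healing and sustained endoscopic remission, and no other SAP rule recovers the discarded endoscopy. The consequence is very small: fewer than one changed outcome per arm is expected, the endoscopic remission difference falls by about 0.06–0.4 points at 10% missing diary scores (half that at 5%), and the power change is negligible. These sizes rest on the assumed uniform timing, diary-missing rate, enrolment mix and full completion.

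Three stronger readings are not supported:
- **That about 14% of endoscopies are exposed.** This needs the ±10-day window. Under the schedule that should cover most completers, the figure is about 2–7%.
- **That the testing sequence is put at risk.** SAP Table 1 lists endoscopic remission first among the key secondary endpoints and SAP 6.4 passes alpha down in order, but the figure fixing that order is not available here. Even if it is tested first, its power moves only from 0.949 to between 0.942 and 0.945.
- **That the comparison is biased toward one arm.** Nothing in the documents suggests that diary gaps differ by arm.

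This is a minor correction, worth making because it is cheap.

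**What to change.** Replace the diary condition in the Table 6 footnote with a date-based one that also covers the biopsy, for which Table 6 names no window. Proposed text:

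*The Week 52 window for endoscopy and biopsy starts on Day 343 for subjects who did not discontinue treatment early and whose EOT (Visit 14 Part 2) date is on or after Day 351, regardless of SF/RB availability.*

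Both conditions are needed. A visit label would not do, because SAP 12.3 disregards the CRF page and Protocol 7.2.2.2 uses the same Visit 14 procedures for early termination. The date alone would admit an early terminator with Part 1 on Day 343 and Part 2 on Days 351–353.

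Subjects who discontinue remain failures under the composite estimand, and endpoints that need SF/RB still fail when those are missing. The cost is one footnote and one programming condition, to be settled before unblinding.

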12.4 Derived Efficacy Endpoints

12.4.1 Total Mayo Score

The Mayo score is a measure of UC disease activity. The total Mayo score ranges from 0 to 12 points and consists of the following 4 subscores, each graded from 0 to 3 with higher scores indicating more severe disease:

- Stool frequency (0-3)
- Rectal bleeding (0-3)
- Findings on endoscopy (0-3)
- Physician’s global assessment (0-3).

The calculation of the total score requires SF subscore and RB subscores, reported by subjects in the PRO UC daily e-diary, and PGA and centrally read endoscopic subscores.

The Mayo SF and RB subscores will be calculated based on each subject’s daily e-diary data recorded over the most recent 3 days (consecutive or nonconsecutive) of the last 10 days prior to the visit excluding the following days: day of any bowel preparation, day of endoscopy, any days between day of bowel preparation and day of endoscopy, and the 2 days after the day of endoscopy. The most recent 3 days’ subscores will be averaged and rounded to the nearest score according to standard rounding rules. Physician’s global assessment and centrally read endoscopic subscores will be collected at MNT baseline

and the Week 52 visit. The total Mayo score is the sum of the 4 subscores, and will be calculated at MNT baseline and at the Week 52 visit. The total Mayo score from the induction baseline is calculated in an identical fashion in the induction studies (SHP647-301 and SHP647-302) and will be carried over for use in the SHP647-303 study.

12.4.2 Composite Score

The composite score is a regulatory authority-recommended measure derived from the Mayo score omitting the PGA subscore and ranges from 0 to 9 points.

12.4.3 Mucosal Healing

Mucosal healing is based on the endoscopic and histological assessment at the Week 52 visit. Mucosal healing is defined by the centrally read endoscopic subscore 0 or 1 (modified, excludes friability) and the centrally read Geboes score of ≤ 2 .

Mucosal healing based on endoscopic and histological assessment at the MNT baseline and Week 52 visit. Mucosal healing is defined by centrally read endoscopic subscore 0 or 1 (modified, excludes friability) and [REDACTED], with lamina propria neutrophils, neutrophils in epithelium, and erosion or ulceration scores of 0.

12.4.4 Total Sign/Symptom Score

Patient-reported UC signs and symptoms data will be collected using a daily e-diary throughout the study. Subjects will be required to enter e-diary data daily. Subjects will enter data on UC signs and symptoms items using an electronic handheld device that will be provided to subjects at the start of the study. Compliance is assessed by site staff at each visit. The site staff will instruct the subject on the appropriate use of the e-diary, particularly when compliance is below 80% (eg, <8 out of 10 diary entries) when compared to the previous visit.

Subjects will be asked to record the following signs and symptom data, as experienced over the previous 24 hours, in the e diary:

- Stool frequency: Number of Bowel Movements (0-99)
- Rectal bleeding severity and frequency: Rectal Bleeding Worst Experience (0-3) and Number of Bowel Movements with Blood (0-99)

- Diarrhea frequency: Number of Loose Bowel Movements (0-99)
- Urgency frequency: Number of Bowel Movements with Urgency (0-99)
- Abdominal pain worst severity: Worst Abdominal Pain Over the Past 24 Hours (0-10)

Note: In the instrument, if the Number of Bowel Movements is entered as 0, then the rest of questions except Worst Abdominal Pain Over the Past 24 Hours question are skipped as they are further questions about the bowel movements. These skipped items will be considered as 0 for analysis purposes.

Subject's signs and symptom average scores at each scheduled visit will be calculated based on data recorded over the most recent 3 days (consecutive or nonconsecutive) of the last 10 days prior to the scheduled visit start date excluding the following days: day of any bowel preparation, day of endoscopy, any days between day of bowel preparation and day of endoscopy, and the 2 days after the day of endoscopy. Daily signs and symptom records will be assigned to visits based on visit window in [Table 6](#). The assessment closest to the planned visit day will be used for analysis at that visit.

Number of bowel movements and rectal bleeding worst experience will be used to determine the Mayo stool frequency and rectal bleeding subscores, which will be used to calculate the total and partial Mayo scores and the composite score. Subject's signs and symptom average scores of number bowel movements with blood, number bowel movements with urgency, number of bowel movements and number of loose bowel movements will be converted to the same scale as shown in [Table 10](#). No conversion will be applied for average scores of worst abdominal pain over the past 24 hours.

Table 10 Proposed Categorized Sign/Symptom Score Conversion Scale

Response	Conversion (applied to each item)
0-2	0
3-5	2.5
6-8	5
9-11	7.5
≥12	10

Total sign/symptom score is the average of the average scores of worst abdominal pain over the past 24 hours and the conversion scale values for number of bowel movements blood, number of bowel movements with urgency, number of bowel movements and number of loose bowel movements, with scale range of 0-10. The categorized and total score scoring systems will be confirmed after database lock according to the UC PRO SAP and are subject to change after the psychometric assessment has been completed.

12.5 Repeated or Unscheduled Assessments of Safety Parameters

Assessments will be assigned to visits based on the date the assessment took place regardless of the completed CRF page. Assessments will be mapped to visits as outlined in [Table 6](#) to Table 9.

If a subject has more than 1 assessment mapped into a given study visit with non-missing results, the assessment closest to the planned visit will be used for analysis. However, all post-MNT baseline assessments will be used for PCI value determination.

12.6 Handling of Missing, Unused, and Spurious Data

12.6.1 Missing Date of End of Treatment

When the date of the end of treatment is missing for a subject, all efforts should be made to obtain the date from the investigator. If it is still missing after all efforts, then the last dose date + 28 days will be used in the calculation of treatment duration.

12.6.2 Missing Date of Ulcerative Colitis Diagnoses

If day of diagnosis date is missing, then the day will be imputed as 1; if both the day and month of diagnosis date are missing, then the day will be imputed as 1 and the month will be imputed as 1 (January).

12.6.3 Missing Date Information for Prior or Concomitant Medications (Therapies/Procedures)

The induction study (SHP647-301 or SHP647-302) imputed dates will be used for prior medications for those collected in induction study.

For prior or concomitant medications collected in SHP647-303, including rescue medications, incomplete (ie, partially missing) start date and/or stop date will be imputed. When the start date and the stop date are both incomplete for a subject, impute the start date first.

12.6.3.1 Incomplete Start Date

The following rules will be applied to impute the missing numerical fields. If the stop date is complete and the imputed start date is after the stop date, then the start date will be imputed using the stop date.

12.6.3.1.1 Missing Day and Month

- If the year of the incomplete start date is the same as the year of the date of the first dose of IP, then the day and month of the date of the first dose of IP in the SHP647-303 study will be assigned to the missing fields.
- If the year of the incomplete start date is before the year of the date of the first dose of IP in the SHP647-303 study, then December 31 will be assigned to the missing fields.
- If the year of the incomplete start date is after the year of the date of the first dose of IP in the SHP647-303 study, then 01 January will be assigned to the missing fields.

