### 5.2.3 Rescue Therapy

Subjects must maintain their stable dose of background UC treatment, unless dose reduction or discontinuation are required due to associated AEs. If a subject requires initiation of a new therapy or increase in glucocorticoids for UC above the SHP647-303 baseline level, the subject should be withdrawn from study treatment and enter the safety follow-up period, and appropriate treatment should be given at the discretion of the investigator.

Subjects who enter the follow-up period will no longer need to abstain from the medications that were prohibited during the baseline and treatment periods. High-dose glucocorticoids and other UC treatments will be allowed. Biologics or nonbiologic immunosuppressants should not be initiated during the safety follow-up period without prior discussion with the sponsor study physician or designee due to the long half-life of ontamalimab.

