6.1 Analyses of Primary Efficacy Endpoint

The primary efficacy endpoint is remission at the Week 52 visit. Remission is defined as a composite score of patient-reported symptoms using daily e-diary and centrally read endoscopy as follows:

- Stool frequency subscore of 0 or 1 with at least a 1-point change from induction (SHP647-301 or SHP647-302) baseline

AND

- Rectal bleeding subscore of 0

AND

- Endoscopic subscore of 0 or 1 (modified, excludes friability), based on centrally read results.

The primary efficacy endpoint will be compared for each active treatment group (25 mg or 75 mg ontamalimab) to the corresponding placebo group (25 mg in induction placebo group or 75 mg in induction placebo group; placebo groups are not pooled) using a Cochran-Mantel Haenszel (CMH) chi-square test stratified by actual status of glucocorticoid use at MNT (SHP647-303) baseline, prior anti-TNF treatment, and the degree of clinical response in the induction studies (whether remission is achieved or not). Subjects with the intercurrent events defined in Section 2.2 and/or with missing remission data at Week 52 will be considered failures and counted as nonresponders. Subjects with treatment failure will also be counted as nonresponders. Subjects with missing induction baseline value in SF subscore will be counted as remission if both SF and RB subscores are 0 and endoscopic subscore are either 0 or 1 at Week 52. The endoscopy score will be based on centrally read results.

The primary endpoint will be tested by the following hypothesis:

$$H_0: \delta = 0$$

$$H_1: \delta \neq 0$$

where δ is the common treatment difference across strata, $j=1$ to m . The common treatment difference is a weighted average of the stratum-specific treatment differences.

The estimate of the common treatment difference along with the corresponding stratified Newcombe 95% CI using the method of Yan and Su (2010) and CMH p-value will be presented for each active treatment group to the corresponding placebo group comparison.

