12.6.3.1.3 Missing Day Only

- If the month and year of the incomplete start date are the same as the month and year of the date of the first dose of IP, then the day of the date of the first dose of IP in the SHP647-303 study will be assigned to the missing day.
- If either the year is before the year of the date of the first dose of IP or if both years are the same but the month is before the month of the date of the first dose of IP in the SHP647-303 study, then the last day of the month will be assigned to the

missing day.

- If either the year is after the year of the date of the first dose of IP or if both years are the same but the month is after the month of the date of the first dose of IP in the SHP647-303 study, then the first day of the month will be assigned to the missing day.

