16.5 Rescue Therapy for Ulcerative Colitis

In order for a medication to be a rescue therapy for UC, it should be reported on the concomitant medication indication specific form.

If the exposure happens in the follow-up period (beginning on the EOT date), then it would not satisfy the criteria, as we are concerned here only about exposure with regards to the estimand, which is during the treatment period.

- **Biologics with immunomodulatory properties**
 - Any exposure after first dose
- **Non-biologics with immunomodulatory properties**
 - **Immunosuppressants**
 - Rule
 - After first dose and up to and including Week 48: any increase from MNT baseline for more than 5 days
 - After Week 48: Any dose above MNT baseline for greater than 1 day
 - MNT baseline
 - Subjects who have at least one dose in the 6 days prior to the dose of study medication at the Week 12 visit in the induction study will be considered to have a MNT baseline dose >0 . The MNT baseline dose to be used for these subjects is the median nonmissing daily dose from these 6 days. Subjects without at least one dose in the 6 days prior to the dose at the Week 12 visit in the induction study will be considered to take a 0 for the dose for the purposes of assessing an increase from MNT baseline
 - **5-ASA**
 - Rule
 - After first dose and up to and including Week 48: any increase from MNT baseline for more than 5 days
 - After Week 48: Any dose above MNT baseline for greater than 1 day
 - MNT baseline
 - Subjects who have at least one dose in the 6 days prior to the dose of study medication at the Week 12 visit in the induction study will be considered to have a MNT baseline dose >0 . The MNT baseline dose to be used for these subjects is the median nonmissing daily dose from these 6 days. Subjects without at least one dose in the 6 days prior to the dose at the Week 12 visit in the induction study will be considered to take a 0 for the dose for the purposes of assessing an increase from MNT baseline
 - Note

- Subjects cannot start the study on the combination of Beclometasone and mesalazine so there would be no switching. It would be only according to the rules.
 - **Other small molecule immunodulatory active agents**
 - Rule
 - Any exposure after first dose
 - **Leukocyte apheresis, other apheresis, and plasma exchange**
 - Rule
 - Any exposure after first dose
 - **Systemic glucocorticoids**
 - **Systemic glucocorticoids given via oral or rectal routes of administration**
 - Rule

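### Partial start dates are imputed against the first dose only, so a UC drug begun after end of treatment can be dated into treatment and flagged as rescue

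*SAP*

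**What the plan says.** SAP 12.6.3 sets the scope: "For prior or concomitant medications collected in SHP647-303, including rescue medications, incomplete (ie, partially missing) start date and/or stop date will be imputed". Drugs collected earlier are carved out: "The induction study (SHP647-301 or SHP647-302) imputed dates will be used for prior medications for those collected in induction study".

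For a partial start date, SAP 12.6.3.1 compares the known parts with the first SHP647-303 dose:

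- Same year (day and month missing) or same month (day missing): the first-dose date is used.
- Earlier year or month: 31 December, or the last day of that month.
- Later year: "incomplete start date is after the year of the date of the first dose of IP in the SHP647-303 study, then 01 January" is assigned. Later month: "then the first day of the month will be assigned to the missing day".

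The only cap is a complete stop date that precedes the imputed start.

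SAP 16.5 defines rescue and limits it to the treatment period: "If the exposure happens in the follow-up period (beginning on the EOT date), then it would not satisfy the criteria". Some drug classes count on any exposure. Immunosuppressants and 5-ASA need more than 5 days above the maintenance (MNT) baseline dose up to Week 48, and oral or rectal systemic glucocorticoids more than 7. After Week 48, more than 1 day is enough for these three. The baseline dose comes from a 6-day window: "Subjects without at least one dose in the 6 days prior to the dose at the Week 12 visit in the induction study" are given a baseline dose of 0.

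The flag feeds the primary endpoint through SAP 6.1: "Subjects with the intercurrent events defined in Section 2.2 and/or with missing remission data at Week 52 will be considered failures". SAP 6.2 does the same for the key secondary endpoints. Protocol 5.2.3 lets UC drugs start in follow-up: "Subjects who enter the follow-up period will no longer need to abstain from the medications that were prohibited during the baseline and treatment periods".

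**The concern.** Two parts of the SAP pull against each other. Appendix 16.5 says a drug started in follow-up is not rescue. Section 12.6.3.1 can move that same drug's start date back before EOT, because it asks only how the known year or month compares with the first dose. Fifty-two weeks of treatment nearly always cross a 1 January, so for a year-only date the move is the usual result.

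A smaller problem lies at the other end of treatment. A background UC drug first entered in SHP647-303, with a known year or month equal to that of the first dose, is dated to the first dose. It then has no dose in the 6-day window, its baseline dose becomes 0, and its unchanged dose counts as an increase.

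In both cases an observed Week 52 response is replaced by failure because of a dating convention. A misdated glucocorticoid could also fall in the 4-week window of the two glucocorticoid-free endpoints.

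**Working it through.** No figure stated in the plan depends on the dating rule, so there is none to reproduce. The check applies the rules to dates.

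**Worked case.** First dose 15 Mar 2019. EOT on Study Day 364, so first dose + 363 days = 12 Mar 2020. The new drug is assumed to be above an MNT baseline dose of 0.

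| True start | Recorded as | Imputed start | Result |
|---|---|---|---|
| 1 May 2020 | 2020 | 01 Jan 2020 | 71 days before EOT: rescue |
| 25 Mar 2020 | Mar 2020 | 01 Mar 2020 | 11 days before EOT, after Week 48: rescue |
| 1 May 2020 | May 2020 | 01 May 2020 | after EOT: correctly not rescue |

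The stop-date rules (SAP 12.6.3.2) can add to this. They anchor to the last dose, here 13 Feb 2020 if the Week 48 dose was given on Day 336. If start and stop are both recorded only as 2020, the course becomes 01 Jan to 13 Feb 2020. That is 44 days, all inside treatment.

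**How often a partially dated post-EOT start is moved.** Assumptions: every first-dose date in 2018 and 2019 equally likely; EOT on Day 364; true start uniform over the days after EOT. Follow-up is 84 days under Amendment 3. It was 16 weeks (112 days) before that (SAP 16.1, note c).

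| Follow-up | Year only known | Day missing |
|---|---|---|
| 84 days | 88.2% dated before EOT | 16.4% dated before EOT |
| 112 days | 84.4% | 12.3% |

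With 84 days, 87.9% and 15.3% also meet a rescue threshold. The average shift to before EOT is about 162 days (year only) and 10 days (day missing).

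Hand check, 84 days:

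- Day missing: on average (30.4 − 1)/2 = 14.7 days of the EOT month remain after EOT, and 14.7/84 = 17.5%. EOT on the 1st is unaffected, which removes (1/30.4) × (29.4/84) = 1.1 points and leaves about 16.4%.
- Year only: the mean start is day 42.5, so 42.5/365 = 11.6% of starts fall in the next calendar year and are dated correctly. That leaves 88.4%, less about 0.3 point for EOT on 1 January.
- For 112 days the year-only figure is 1 − 56.5/365 = 84.5% before that small correction.

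**Background drug first entered in SHP647-303.** Same first-dose date. A true start of 20 Jan 2019 recorded as 2019 becomes 15 Mar 2019, so the baseline dose is 0 and the drug counts as rescue. Recorded as 2018 it becomes 31 Dec 2018, and Feb 2019 becomes 28 Feb 2019; both stay before treatment. If true starts are uniform over the 84, 365 or 1,095 days before first dose, the share moved to the first dose is 88%, 50% or 17% (year only) and 18%, 4% or 1% (day missing).

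**Size per record.** With 366 enrolled and the planned mix, 366 × 592/696 = 311 subjects come from active induction. Over four arms that is 77.8 per arm, so one false flag moves an arm's rate by 1/77.8 = 1.3 points.

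**The case against.** The strongest objection is that very few subjects can be affected:

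- Subjects who stop before Week 52 are already nonresponders, because discontinuation is part of the variable (SAP 2.2).
- Subjects who enter SHP647-304 have no follow-up in this study, and drugs started after the first SHP647-304 dose are held in that database (SAP 5.5).
- What remains is a Week 52 responder who did not roll over, started a UC drug within weeks, and has a partial date that survived data queries. A site that knows only the year of so recent a start would be unusual.

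All of this stands. It limits the size but does not remove the conflict between the two sections.

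A second objection is that early imputation is deliberately conservative. That is reasonable for a drug that may have started on treatment. It is no reason to count a drug that other recorded information places in follow-up, which SAP 16.5 excludes.

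Three stronger readings are tempting, and the documents do not support them:

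- *The rule pulls the treatment difference toward zero.* A false flag on a placebo responder widens the difference. The direction depends on where the flags fall, which is unknown.
- *Background UC drugs in general are scored as rescue.* Drugs collected in induction keep their induction dates, and Protocol 5.1 expects ongoing treatment to have been recorded there. Earlier years or months are dated before treatment.
- *Most follow-up drugs are misdated.* The 88% applies only to starts for which nothing but the year is known. A drug whose known month follows the EOT month, or whose known year follows the EOT year, is dated correctly.

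**Conclusion.** The point holds as a gap in the start-date rules. They apply to rescue medications, never consult EOT, and can contradict the treatment-period limit in SAP 16.5. The result reaches the primary and all key secondary endpoints as nonresponse.

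Of partially dated post-EOT starts, about 16% (day missing) or 88% (year only) are affected with 84 days of follow-up, and about 12% or 84 to 85% with 112 days. These shares rest on uniform first-dose and start dates and on EOT at Day 364. The number of such records is not given and is probably small. Each false flag is worth about 1.3 points in an arm of about 78, itself an estimate from the planned mix. No direction of bias can be claimed.

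The baseline case is narrower: it needs a UC drug missed in induction and a known year or month equal to that of the first dose.

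The correction is worth making because it is cheap and concerns the primary endpoint. It should be settled before unblinding; afterwards, redating a record would be a choice made with treatment known.

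**What to change.** Add to SAP 12.6.3.1, for the rescue and MNT baseline dose derivations only:

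1. If the known date parts allow a start on or after the EOT date, and the drug was first reported after the Week 52/ET visit, impute the start no earlier than the EOT date.
2. If a drug first entered in SHP647-303 is recorded as ongoing at the baseline visit, and the known parts allow a start before the first dose, treat it as taken in the 6-day baseline window at its recorded dose.
3. Never override a known month or year. Keep the current rule for all other partial dates.

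The third sentence matters. With EOT on 12 Mar 2020, a drug recorded as Jan 2020 stays in January even if first reported at the follow-up visit, so a genuine rescue is not erased. The second is worded as use in the window, not as a date 6 days before first dose. Such a date would leave the recorded month whenever the first dose falls on days 1 to 6 (6/30.4, about 20% of dates).

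Cost: three SAP sentences and a programming check. Concomitant medication is collected at each visit (Protocol Table 1), but nothing says the analysis data hold the visit of first report, so a few site queries may be needed. The rescue flag becomes slightly less conservative for these few records.
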